## 1.0 Background

Bronchopulmonary dysplasia (BPD) is the most common chronic lung disease in preterm infants (PI). BPD is defined as requirement for additional oxygen at 36 weeks corrected gestational age (CGA) in infants born with a birth weight < 1500 g and GA < 32 weeks. Pulmonary hypertension (PH) develops in 25-37% of patients with BPD and is associated with significant morbidity/mortality(1).Multiple factors contribute to the development of BPD associated PH (BPD\_PH). Preterm birth causes disruption in pulmonary vascular growth that leads to decreased vascular surface area that increases pulmonary vascular resistance (PVR). Increased PVR leads to altered vasoreactivity and structural remodeling with intimal hyperplasia and increased muscularization of the small pulmonary arteries. There is no definite treatment for BPD\_PH.

**Nitric Oxide:** Nitric Oxide (NO) is a potent pulmonary vasodilator. Endothelial Nitric oxide synthase (eNOS) mediates production of NO from L-Arginine. L-citrulline is a precursor for L-arginine. L-Arginine is a precursor of nitric oxide (NO). Nitric oxide (NO) is produced in the pulmonary arterial endothelial cells (PAECs) from L-arginine by an enzyme endothelial nitric oxide synthase (eNOS). NO is a signaling molecule which leads to dilatation of lung blood vessels and decreases pulmonary vascular resistance, leading to decreased pulmonary hypertension. L-citrulline is an end-product of this reaction and it recycles back to form L-arginine via a two-step enzymatic pathway (figure 1) involving arginosuccinate synthase (ASS) and arginosuccinate lyase (ASL).

**Arginine and citrulline in infants with BPD\_PH:** In infants with BPD\_PH, there are decreased levels of L-arginine & L-citrulline with decreased production of NO (measured by urinary nitrates & nitrites) leading to increased pulmonary vascular resistance. It is suspected that genetic variations in enzymes involving citrulline synthesis may contribute to the susceptibility to develop pulmonary hypertension(2). A cross-sectional pilot study by Montgomery et al reported that L-citrulline levels < 29 µmol/L predicted BPD\_PH with 100% sensitivity and 75% specificity(3).

**Supplementation of citrulline and PVR:** Fike et al showed that oral supplementation with L-citrulline increases vascular NO production and attenuates the development of elevated pulmonary vascular resistance (PVR) in a newborn piglet model of chronic-hypoxia induced pulmonary hypertension(4). In a newborn rat model of hypoxia-induced BPD, subcutaneous injection of L-citrulline decreased pulmonary vascular remodeling and reduced right ventricular hypertrophy (both of these are markers of pulmonary hypertension)(5). A Phase 2 clinical trial of L-citrulline in pediatric patients with sickle cell disease showed decreased vascular complications and improvement in overall well-being(6). L-citrulline has been used in post cardio-pulmonary bypass patients and it has been shown that post-operative pulmonary hypertension did not develop in children who had naturally elevated citrulline levels or who achieved plasma levels greater than 37 µmol/L with oral citrulline supplementation(7).

[figure not shown]

Figure 1. Urea cycle. Adapted from American Journal of Physiology, March 2015.

Why oral L-citrulline: In in-vitro studies, L-arginine promotes NO production (See Figure 1) but in in-vivo studies (animal models of PH), oral L-arginine did not increase NO production due to hydrolysis of L-arginine by arginases present in enterocytes in gastrointestinal tract and hepatocytes, leading to decreased bioavailability of oral Larginine. Alternatively, oral L-citrulline (precursor for L-arginine figure 1) can be used to increase L-arginine & NO production. After being produced and released into the circulation by enterocytes, L-citrulline passes through the liver without major metabolism. Cells in the proximal tubules of the kidney take up and metabolize some of the circulating L-citrulline into L-arginine in urea cycle via enzymes arginosuccinate synthase and arginosuccinate lyase. Therefore, a significant portion of the L-citrulline produced by enterocytes reaches the systemic circulation as compared to L-arginine. PAECs express the enzymes ASS and ASL and can use L-citrulline to produce NO. There is some evidence suggesting that co-localization of these enzymes with eNOS in the plasmalemmal caveolae (invaginations of plasma membrane in the pulmonary arterial endothelial cells) may allow L-citrulline-induced increases in L-arginine to be directly channeled to eNOS rather than equilibrating with intracellular levels(2).

In-vitro and In-vivo studies of L-citrulline supplementation in newborn piglets showed increased NO production and decreased PH in newborn piglets. These studies also showed that treatment with L-citrulline reduced superoxide generation, increased NO production as well as helped with eNOS re-coupling which is the active form of eNOS (dimeric form of eNOS is the active form).

**Arginine as essential amino acid:** Under routine conditions arginine is not an essential amino acid but is considered an essential amino acid in neonates, particularly under stress, infection and prematurity. In neonatal period (suckling period), the major source for endogenous arginine biosynthesis is from citrulline in the intestine.

**Source of L-arginine in preterm infants:** Routinely, extremely premature infants receive nutrition as total parental nutrition (TPN i.e. infants get infusion of protein, fat and carbohydrate via central venous line) that contains L-arginine (approximately 1mg/1mL) to metabolize ammonia via urea cycle. PIs receive adequate amount of intra venous arginine from TPN. Routinely, PIs are started with small volumes of enteral feeds which are increased slowly overtime. TPN is slowly decreased as enteral feeds are increasing. As the TPN is going down, intra venous L-arginine intake also drops down and ultimately when the PI are off TPN, they don't get any IV supplemental L-arginine.

Why long term IV arginine not possible in preterm infants: In PI, the major cause of late onset infection (after 7 days of age) is central line related infection that is why central line is taken out as soon as infant reaches full feed.

Why oral citrulline: Enteral feeds (formula as well as breast milk) is poor source of arginine. Once PIs are on full enteral feed, an enteral feed is the only source of arginine. Interestingly, 40% of enteral arginine gets metabolized by arginase enzyme present in intestine. We speculate that plasma levels of arginine drop once TPN is discontinued and infants are on full feeds. Oral L-arginine has poor bio-availability that is why oral L-arginine supplementation does not increase blood levels of arginine. Since oral citrulline has high bioavailability, the best way to increase serum arginine levels is by oral citrulline supplementation. Oral supplementation of L-citrulline in preterm infants once they are off TPN will likely to increase arginine levels and NO production.

**Safety of oral citrulline:** L-citrulline has been safely used for decades in patients with urea cycle defects. It has been used in pediatric patients with sickle cell disease and in infants undergoing cardiac surgery. No side effects were reported in these studies. In a study in newborn rats exposed to hyperoxia, L-citrulline caused a marked increase in arginase-2 expression in the lungs and this could have an impact on lung development and remodeling(5). However, this is only a theoretical risk.

Oral L-citrulline supplementation may prevent and/or decrease the severity of BPD\_PH. Since oral L-citrulline supplementation has never been studied in preterm infants before, the side effect profile and appropriate dosing is still unknown. In this pilot study, we will determine the safety profile, efficacy and appropriate dosing of oral Lcitrulline in preterm infants. In future, information from this study will be utilized to conduct a randomized placebo-controlled trial to evaluate the role of L-citrulline supplementation in treating BPD\_PH.

## 2.0 Rationale and Specific Aims

### Specific Aim 1 -

To test the hypothesis that enteral supplementation of L-citrulline (a precursor of Larginine) is effective in increasing plasma L-arginine and L-citrulline concentrations in premature infants with increased NO production.

Intervention: Enteral L-citrulline supplementation

Rationale & feasibility - L-arginine is a precursor of NO production. Premature infants who develop BPD\_PH have lower levels of L-arginine and L-citrulline, decreased NO production, eventually leading to the development of pulmonary hypertension. Oral arginine is poorly bioavailable hence oral L-citrulline will be used (precursor of L-arginine, see figure below). We expect L-citrulline supplementation in premature infants will increase plasma L-arginine and L-citrulline concentrations and increase NO production (measured indirectly by urinary end-products).

## Specific Aim 2 -

To determine the safety of oral L-citrulline supplementation in premature infants. Increased production of NO may lead to systemic hypotension by its vasodilator effect. All infants in the neonatal ICU are always on electronic monitors and monitored for heart rate, oxygen saturations and BP. We will continuously monitor all infants for systemic hypotension. Significant hypotension will be defined as a 25% drop in systemic mean blood pressure (measure by non-invasive blood pressure monitoring). Other parameters to be recorded include increase in oxygen requirements/escalation in respiratory support, metabolic abnormalities (on routine glucoses and electrolyte monitoring), effect on bone-marrow by weekly complete blood counts (done routinely on preterm infants).

## Specific Aim 3 –

To determine the dose of enteral L-citrulline required to increase plasma level of > 37  $\mu$ mol/L.

We will use three doses (low, medium and high) of enteral L-citrulline as follows -**Group 1**: *Low dose* 50 mg/kg given two times a day (100 mg/kg/day) for total 7 days. **Group 2**: *Medium dose* 100 mg/kg given two times a day (200 mg/kg/day) for total 7 days

Group 3: High dose 150 mg/kg given two times a day (300 mg/kg/day) for total 7 days

Rationale:

Previous studies in patients undergoing cardiac surgery have shown that post-operative pulmonary hypertension did not develop in patients with citrulline level > 37  $\mu$ mol/L(7). A cross-sectional study reported that citrulline levels < 29  $\mu$ mol/L was associated with BPD\_PH (100% sensitivity and 75% specificity) hence this may be used as a screening tool for BPD\_PH(3). We will use the higher levels of citrulline of the reported levels as our goal (>37 $\mu$ mol/L). We will supplement infants with 3 different dosages and check serum levels to see what dose is required for to achieve optimal plasma level of citrulline (>37 $\mu$ mol/L).

## 3.0 Inclusion/Exclusion Criteria

Inclusion criteria - Subjects must meet all of the inclusion criteria in order to be eligible to participate in the study.

1. Infants  $\leq$  30 weeks' gestational age born at UTMB, Galveston.

2. Parents have provided informed consent/assent in a manner that is approved by the IRB

The reason for the inclusion of such a vulnerable population is that BPD is primarily a disease of premature infants and PH is a common complication of BPD. It is also a condition with high mortality and there still exists significant confusion over appropriate management. Being a randomized controlled trial, the study does add certain risks to the subjects: frequent blood draws (minimized by using discarded blood and urine samples) . Since diagnosis and management of BPD\_PH is not currently standard of practice, we will not be withholding any beneficial therapy. The present research protocol will not interfere in the management of the preterm infants as treating neonatal team will be taking all management decisions. All risks will be explained to the parents and written informed consent will be obtained from the parents of all subjects.

Exclusion criteria - Subjects meeting any of the exclusion criteria at baseline will be excluded from study participation.

1. Known congenital or chromosomal anomalies.

2. Congenital heart disease affecting cardio-respiratory system (other than PDA, PFO or ASD)

3. NEC, sepsis, or any condition requiring surgery prior to recruitment

### 4.0 Treatment Assignment/Randomization

**Recruitment** - Parents of all eligible infants will be approached by research investigator to discuss about the study & research protocol in detail. All questions & concerns will be answered in very simple language & parents will be given written consent form to read. Within 24 to 48 hours, the parents will be approached again to discuss & explain any question they have. We expect around 70 - 75% success in the recruitment. Every year, we deliver around 50 infants ( $\leq$ 30 weeks' gestation). We hope to recruit our desired sample of 42 infants (14 in each study group) within 12 months.

**Sample size:** 14 preterm infants will be randomized to each group (total sample 42) A sample size of 14 at each group (low, median, and high dose) for efficacy endpoint will reach a power of 0.80 to detect an effect size of 0.5 based on one-way ANOVA with a 0.05 significance level. A sample size of 11 at each group for safety endpoint will reach a power of 0.92 at a 0.05 significant level for an equivalence test of means using two onesided tests, when the true difference between the means is 0.0 mmHg, the standard deviation is 10.0 mmHg, and the equivalence limits are -15.0 mm Hg and 15.0 mmHg.

**Randomization:** Adaptive randomization method will be used – each new participant will be sequentially assigned to a particular treatment group by taking into account the previous assignments of participants. For example, first recruit will be Group 1, second Group 2, third Group 3, fourth Group 1 and so on. The study will be blinded to the nurses and parents. If patients complete 12/14 doses of the treatment, they will be analyzed in the treatment arm.

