## 7.0 Adverse Events or Unanticipated Problems involving Risk to Participants or Others

Immediate risks: Increased NO production may theoretically lead to systemic hypotension – all these infants will be in an intensive care setting with cardiac monitors and continuous blood pressure monitoring. Significant hypotension will be defined as a 25% drop in systemic mean blood pressure from baseline (average mean arterial pressure in the week prior to starting study drug).

Local irritation to skin or eyes is possible with direct contact with study drug.

Long-range risks: A theoretical risk of adverse impact on structural remodeling of pulmonary architecture vis increase in arginase two expression in lungs (seen in rats).

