### Rationale:

Children with urea cycle defects have been treated with L-citrulline for decades and showed no evidence of toxicity. Previous studies in literature have not reported any significant adverse effects. The benefit of treatment (helping treat or prevent BPD\_PH) far outweighs the risks since this condition is associated with significant morbidity/mortality and no preventative measures exist at this time. The study drug has already been tested on animal models and there are no alternatives to studying the safety, efficacy and dosing in preterm infants.

ICH E6 defines an AE as any untoward medical occurrence in a patient or clinical investigation subject administered a pharmaceutical product regardless of its causal relationship to the study treatment. An AE can therefore be any unfavorable and unintended sign (including an abnormal laboratory finding), symptom, or disease temporally associated with the use of medicinal (investigational) product.

All AEs including local and systemic reactions not meeting the criteria for "serious adverse events" should be captured on the appropriate CRF. Information to be collected includes event description, time of onset, clinician's assessment of severity, relationship to study product (assessed only by those with the training and authority to make a diagnosis, which would include MD, PA, Nurse Practitioner, DO, or DDS), and time of resolution/stabilization of the event. All AEs occurring while on study must be documented appropriately regardless of relationship. All AEs will be followed to adequate resolution.

Any medical condition that is present at the time that the patient is screened will be considered as baseline and will not be reported as an AE. However, if it deteriorates at any time during the study, it should be recorded as an AE.

All AEs must be graded for severity and relationship to study product.

**Severity of Event:** All AEs will be assessed by the clinician using a protocol defined grading system. For events not included in the protocol defined grading system, then the following guidelines will be used to quantify intensity.

- Mild: events require minimal or no treatment and do not interfere with the patient's daily activities.
- Moderate: events result in a low level of inconvenience or concern with the therapeutic measures. Moderate events may cause some interference with functioning.

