- Severe: events interrupt a patient's usual daily activity and may require systemic drug therapy or other treatment. Severe events are usually incapacitating.
- Life threatening: any adverse drug experience that places the patient or subject, in the view of the investigator, at immediate risk of death from the reaction as it occurred, i.e., it does not include a reaction that had it occurred in a more severe form, might have caused death.

Changes in the severity of an AE should be documented to allow an assessment of the duration of the event at each level of intensity to be performed. Adverse events characterized as intermittent require documentation of onset and duration of each episode.

Protocol Grading System for Hypotension:

Mild: Drop in systemic mean arterial pressure (MAP)  $\leq$  10% from baseline

Moderate: Drop in systemic mean arterial pressure (MAP)  $\leq$  25% from baseline

Severe: Drop in mean arterial pressure (MAP) > 25% from baseline

Life threatening: Severe hypotension requiring 2 or more inotropes (Dopamine, Epinephrine, Norepinephrine)

**Relationship to Study Products:** If there is any doubt as to whether a clinical observation is an AE, the event will be reported. All AEs must have their relationship to study product assessed using the terms: associated or not associated. In a clinical trial, the study product must always be suspect. To help assess, the following guidelines are used.

- Associated The event is temporally related to the administration of the study product and no other etiology explains the event.
- Not Associated The event is temporally independent of study product and/or the event appears to be explained by another etiology.

**Serious Adverse Event (SAE)**: An SAE in our study will be defined as an AE that meets one of the following conditions:

- Death during the period of protocol defined surveillance
- Life-threatening event (defined as a subject at immediate risk of death at the time of the event) significant hypotension requiring 2 or more inotropes

- Results in a persistent or significant disability/incapacity: Intraventricular hemorrhage Grade III or more, Necrotizing enterocolitis requiring surgery, Retinopathy of prematurity requiring surgery
- Significant lab abnormalities: Thrombocytopenia < 50,000

All SAEs will be:

- recorded on the appropriate SAE CRF
- followed through resolution by a study clinician
- reviewed and evaluated by a study clinician

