## 8.0 Study Withdrawal/Discontinuation

### **Reasons for Withdrawal**

A study subject will be discontinued from participation in the study if any of the following occur:

- Unacceptable toxicity or adverse event (AE): Drop in systemic mean blood pressure > 25% from baseline
- Unacceptable laboratory abnormalities: Thrombocytopenia < 50,000 not explained by other co-existing conditions
- Intercurrent illness, or other medical condition or situation occurs such that continued participation in the study would not be in the best interest of the subject in the opinion of the treating investigator, for e.g. necrotizing enterocolitis requiring subject to be made NPO.
- Development of any exclusion criteria
- Parents withdraw consent to continue in the research for any reason

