### Handling of Withdrawals

Any subjects that withdraw from the study will continue to receive standard of care treatment according to our NICU protocols and will continue to be followed clinically by the primary neonatologist. Safety data from these subjects will be presented to the DSMB for evaluation.

Since this is a pilot study, we will not need to replace subjects in case of withdrawals.

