### 9.0 Statistical Considerations

Study design: Single-center Pilot dose-ranging study

Study population: Premature infants admitted to the Neonatal intensive care unit at UTMB, Galveston.

Rationale: L-citrulline has been shown to increase NO production in neonatal pigs. The use of L-citrulline in premature infants may help increase NO and prevent pulmonary hypertension that develops due to chronic lung disease. Even though L-citrulline has been used safely in infants and children for urea cycle disorders, its dosage, efficacy and safety have not been evaluated in premature infants. Therefore, a pilot dose-ranging study is essential.

There will be 3 study groups in this Phase I trial:

Group 1 (Low dose): 100 mg/kg/day of L-citrulline Group 2 (Medium dose): 200 mg/kg/day of L-citrulline Group 3 (High dose): 300 mg/kg/day of L-citrulline

Sample size: A sample size of 14 at each group (low, median, and high dose) for efficacy endpoint will reach a power of 0.80 to

detect an effect size of 0.5 based on one-way analysis of variance (ANOVA) with a 0.05 significance level. The sample size calculation was based on the following expected mean  $\pm$  SD citrulline concentrations in plasma according to the study from Schwedhelm et al:

Low dose group:  $19 \pm 4 \ \mu mol/L$ Medium dose group:  $21 \pm 4 \ \mu mol/L$ High dose group:  $45 \pm 5 \ \mu mol/L$ 

Primary outcome:

1. Increase in plasma L-citrulline levels and increased NO production (measured indirectly via urinary breakdown products)

Secondary outcomes:

- 1. To determine safety of enteral L-citrulline supplementation in premature infants.
- 2. To determine the dose of enteral L-citrulline needed to increase plasma level of citrulline > 37 mol/L.

Data will be collected from electronic medical records. Measurements will be recorded in a password protected computer on an excel sheet.

A Data Safety Monitor Board (DSMB) as mentioned in section 7.0 will be reviewing safety data every 4 months.

The data will be analyzed at the end of data collection for all subjects who meet the inclusion criteria. SPSS version 24 will be used for data analysis. SAS procedures, linear models, repeated measures analysis of variance (ANOVA) & logistic modeling for receiver operator curve generation (significance p<0.05) will be used. The UTMB Clinical trials studio will be involved to assist in statistics.

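### The one stated safety test compares means between treated doses, so it cannot show a blood-pressure fall common to all doses and gives no rate for the protocol's own hypotension event

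*Combined protocol and SAP*

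**What the plan says.** Safety is Specific Aim 2 in section 2.0, and section 9.0 lists it as a secondary outcome: "To determine safety of enteral L-citrulline supplementation in premature infants".

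The blood-pressure harm is defined for the individual infant. Section 7.0 states: "Significant hypotension will be defined as a 25% drop in systemic mean blood pressure from baseline", where baseline is that infant's own mean arterial pressure averaged over the week before the first dose. The grading scale in section 7.0 has "Severe: Drop in mean arterial pressure (MAP) > 25% from baseline", and section 8.0 ends participation for "Drop in systemic mean blood pressure > 25% from baseline".

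Capture of events is covered. Section 7.0 requires that "All AEs occurring while on study must be documented appropriately regardless of relationship". For withdrawn infants, section 8.0 adds: "Safety data from these subjects will be presented to the DSMB for evaluation". Section 9.0 has the DSMB look at safety data every four months.

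The only inferential statement about safety is the sizing sentence in section 4.0: 11 per group, power 0.92, at a 0.05 "significant level for an equivalence test of means using two onesided tests", true difference 0, SD 10 mmHg, limits ±15 mmHg. It names neither the variable nor the groups compared; blood pressure is inferred from the units. Section 9.0 repeats the efficacy sizing but not this test. It assigns the one-way ANOVA to the plasma and urine measures and describes the paired t-test alongside them. Its remaining list of methods is not linked to safety.

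**The concern.** The stated test and the stated harm are different quantities. The test asks whether two doses have similar means. The harm is a large fall in one infant relative to its own past. All three groups receive L-citrulline, so a fall produced by every dose cancels out of each between-dose difference. That is a plausible pattern if the drug acts by vasodilation, which is the risk the protocol names.

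If the plan is followed as written, the blood-pressure part of Aim 2 would be answered by a conclusion of equivalence between doses. That conclusion says nothing about how often infants became hypotensive or how precisely the rate is known. The background section says this pilot is meant to inform a placebo-controlled trial, which would need that rate and its uncertainty.

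The denominator is also unsettled. Sections 4.0 and 6.0 count an infant as treated or complete after 12 of 14 doses, and section 9.0 excludes infants without the blood sample, although it also states intention-to-treat. An infant withdrawn early for hypotension could fail both conditions.

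**Working it through.** **1. The plan's own figure.** Inputs from section 4.0: n = 11 per group, SD 10, limits ±15, true difference 0, 0.05 for each one-sided test.
- SE = 10 × √(2/11) = 4.264, and 15 / 4.264 = 3.518.
- With 20 degrees of freedom the critical t is 1.725. Power = 1 − 2 × F(1.725), where F is the noncentral t distribution with noncentrality 3.518. The result is 0.920, as stated.
- Alternatives at n = 11 fit less well: 0.025 per side gives 0.834, a paired or one-sample test with SD 10 gives 0.997, and a normal approximation to the two-sample test gives 0.939.

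So 0.92 describes one two-sample comparison, that is, one dose against another.

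**2. A fall common to all doses.** If every dose lowers the mean by δ, the difference is (μ₁ − δ) − (μ₂ − δ) = μ₁ − μ₂. δ disappears whatever the baseline, and whether the variable is pressure or change in pressure. Simulation (200,000 replicates, SD 10, limits ±15, n = 14):

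| Scenario | One pair passes | All three pairs pass |
|---|---|---|
| No fall | 0.974 | 0.932 |
| 12 mmHg fall in every infant | 0.973 | 0.931 |
| 12 mmHg fall in 4 infants on every dose | 0.952 | 0.880 |

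In the last row, if those falls are the events, the proportion is 12/42 = 28.6% (exact 95% interval 15.7% to 44.6%).

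For the event itself, assume a baseline of 40 mmHg (not in the documents), so that 25% is 10 mmHg, and an SD of within-infant change of 5 to 10 mmHg. A common 12 mmHg fall puts Φ((12 − 10)/SD) = 66% to 58% of infants past the limit, against Φ(−10/SD) = 2% to 16% with no fall.

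**3. Falls confined to one dose.** Four infants on one dose fall 12 mmHg (30% of the assumed 40 mmHg), fully reflected in the analysed value:

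| n per group | Comparison | None affected | 4 affected |
|---|---|---|---|
| 14 | one pair | 0.974 | 0.884 |
| 14 | affected dose against both others | 0.952 | 0.808 |
| 11 | one pair | 0.920 | 0.724 |
| 11 | affected dose against both others | 0.857 | 0.586 |

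For assumed baselines from 30 to 60 mmHg, the both-others figure with four affected runs from 0.876 down to 0.598 at n = 14, and from 0.704 down to 0.318 at n = 11. Part of the tolerance comes from the margin: with ±10 and n = 14 the both-others figure is 0.455 with none affected and 0.240 with four.

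**4. Precision available for the event.** With no events the exact two-sided 95% upper limit is 1 − 0.025^(1/n): 23.2% for n = 14 and 8.4% for n = 42. Four events in 14 give 8.4% to 58.1%.

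**5. Precision for within-infant change.** If the SD of change is 10 mmHg (an assumption), the 95% half-width is 2.02 × 10/√42 = 3.1 mmHg pooled and 2.16 × 10/√14 = 5.8 mmHg per dose. A common 12 mmHg fall would be plain.

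**6. Why the event needs a fixed rule.** Suppose no drug effect, baseline 40 mmHg and independent readings, all assumptions. The chance that an infant has at least one reading more than 25% low is 1 − (1 − p)^m, with p = Φ(−10/SD). At 8 readings a day for 7 days (m = 56) this is 29%, 72% or 94% for a reading SD of 4, 5 or 6 mmHg. At 4 a day (m = 28) it is 16%, 47% or 75%. Correlated readings would lower these figures.

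**The case against.** The strongest reply is that nothing is hidden. An infant whose pressure falls by more than 25% is graded severe, taken off study drug and reported. If all infants fell that far, all would be discontinued, whatever the equivalence test said. Threshold and baseline are already fixed, so a count per dose could be drawn from the adverse-event records. This is a small pilot with safety as a secondary outcome, and the intervals will be wide.

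Much of this stands. A reader might infer from the mismatch that hypotension could go unnoticed; the documents do not support that, because sections 7.0 to 9.0 provide for grading, recording, withdrawal and DSMB review. A reader might also infer that the test is blind to trouble on one dose. It is not: at n = 11, the size to which 0.92 applies, four affected infants cut the chance of passing against both other doses from 0.86 to 0.59. Nor is 0.92 miscalculated.

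What does not stand is that records replace an analysis. They do not settle who is in the denominator, what counts as a qualifying fall, or how uncertainty is reported. The cancellation of a common fall is exact and depends on no assumed value.

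**Conclusion.** The point holds as a gap in the final safety analysis, and it should be corrected. The one stated safety method cannot detect a fall shared by all doses and does not estimate the event the protocol calls significant. The shared-fall result is algebraic; the 0.93 pass probability with or without it rests only on section 4.0's SD and limits with n = 14. The one-dose results are secondary: they are modest at n = 11, depend on an assumed baseline, and partly reflect the wide margin.

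Two limits apply. That the test is between doses is inferred from the wording about groups and from the match to 0.92. Part of section 7.0 was not available, and section 9.0 points to section 7.0 for the DSMB. It would therefore go too far to say that no rate is planned anywhere; the claim is confined to the text that could be read.

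**What to change.** In section 9.0:
- Make the main blood-pressure safety analysis the number and proportion of infants who, between first dose and Day 7, have a hypotension event graded severe or worse under section 7.0 or are withdrawn for it under section 8.0. Report it per dose and pooled, with exact (Clopper-Pearson) 95% intervals.
- Use as denominator all infants given at least one dose, including those with fewer than 12 doses, withdrawn, or without a Day 7 sample.
- Apply one fixed rule for a qualifying fall to every infant, for example confirmation on a repeat reading, so that isolated noisy readings are not counted.
- Add the within-infant change in mean pressure from the prior-week average, per dose and pooled, with 95% intervals. This is the analysis that detects a fall common to all doses.
- Keep the between-dose equivalence test as supporting, and name its variable.

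In section 4.0, state that 0.92 applies only to the between-dose comparison of means, and that 0/14 excludes event rates above 23.2% and 0/42 above 8.4% (two-sided 95%).

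The cost is a few sentences, plus a repeat cuff reading if confirmation is the chosen rule. No extra infants are needed, and dosing, grading and withdrawal rules are unchanged. The intervals will be wide, and without an untreated group spontaneous falls cannot be separated from a drug effect.
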